3.2. Part 1: Dose Escalation

3.2.1. Cohort Dose Escalation

Dose-escalation decisions for KZR-261 will be guided by the i3+3 design ([Zhou and Ji, 2020](#); [Liu et al., 2020](#)) with the targeted DLT rate $p_r=0.3$ and the equivalence interval (EI) = [0.25, 0.35]. The number of subjects that will be enrolled at each dose level varies, with a minimum of 2 subjects, a typical cohort size of 2-4, and 6 to approximately 12 subjects dosed at the putative MTD or MAD. [Table 1](#), generated using [REDACTED], lists the decisions for up to 12 subjects treated at a given dose.

The columns in [Table 1](#) represent the number of subjects enrolled at a given dose, and the row represents the number of DLTs at the same dose. The dose-escalation decisions are as follows: E: Escalate to the next higher dose; S: Stay at the current dose; D: De-escalate to a lower dose; DU: De-escalate to a lower dose, the current dose may not be used again pending advice of the Safety Review Committee (SRC). The determination of the dose escalation or dose de-escalation will be based on the algorithm as described in [Table 1](#). Safety data from all subjects enrolled in each cohort will be reviewed to confirm occurrence of any DLTs experienced during the first cycle (DLT assessment period) to determine whether to expand the current cohort or to initiate enrollment into the next cohort. Note that if 2 out of 2 subjects have DLTs when treated at the lowest dose level the Sponsor, based on recommendations from the SRC, may choose to enroll one more subject, amend the study to allow a revised dose regimen (ie, enroll subjects at a lower dose or modify the dosing schedule), or terminate the study.

Table 1: Decision Table in i3+3 Design for up to 12 Subjects Treated at a Given Dose with the Targeted DLT Rate $p_T=0.3$ and the Equivalence Interval (EI) = [0.25, 0.35]

		Number of Subjects											
		1	2	3	4	5	6	7	8	9	10	11	12
Number of Subjects with DLTs	0	E	E	E	E	E	E	E	E	E	E	E	E
	1	S	S	S	S	E	E	E	E	E	E	E	E
	2		DU*	D	D	S	S	S	S	E	E	E	E
	3			DU	DU	D	D	D	D	S	S	S	S
	4				DU	DU	DU	D	D	D	D	D	S
	5					DU	DU	DU	DU	DU	D	D	D
	6						DU	DU	DU	DU	DU	DU	D
	7							DU	DU	DU	DU	DU	DU
	8								DU	DU	DU	DU	DU
	9									DU	DU	DU	DU
	10										DU	DU	DU
	11											DU	DU
	12												DU

E: Escalate to the next higher dose; S: Stay at the same dose; D: De-escalate to a lower dose; DU: De-escalate to a lower dose, the current dose may not be used again pending advice of the Safety Review Committee. The dose level for de-escalation will be selected by the SRC.

* If at the first dose level, Sponsor can choose to enroll one more subject, amend the study to allow a revised dose regimen (ie, enroll subjects at a lower dose or modify the dosing schedule), or terminate the study based on their discretion and in consultation with the SRC.

Source: [\(Liu et al., 2020\)](#)

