3.2.2. Intra-subject Dose Escalation

Intra-subject dose escalation will be permitted after consultation with the Medical Monitor and in the following circumstance only:

- Subject must have completed at least two 28-day cycles of treatment (Cycles 1 and 2).
- Subject who experienced an AE* \leq Grade 3 with resolution to Grade 1 or baseline in the setting of a documented tumor response or stable disease over 2 consecutive assessment timepoints. For subjects who experienced a Grade 3 AE, the Investigator and Medical Monitor should come to an unequivocal consensus that the potential benefit of an increase in dose is likely to outweigh the risks.
- Subject must not have experienced a DLT.

- Subject must not have experienced a dose reduction for purposes of managing AEs and/or laboratory abnormalities.
- The higher dose cohort to which the subject would be escalated has been deemed by the SRC to be safe and adequately tolerated.

** AEs must be assessed as unrelated to study treatment, such as intercurrent illness or concomitant medication. AEs that are assessed as related to study treatment would disqualify a patient from dose escalation.*

3.2.3. Definition of Dose-Limiting Toxicity for Part 1

A DLT is defined as an AE or abnormal laboratory value that occurs during the first 28 days of treatment (Cycle 1) and meets the criteria listed below, unless it is assessed to be related to the disease under study, intercurrent illness, or concomitant medications.

Toxicities will be assessed by the Investigator using the NCI CTCAE v5.0. AEs that are not listed in the NCI CTCAE are to be assessed using the criteria in [Section 9.1.2](#). The attribution of an AE is to be assessed by the Investigator using the criteria in [Section 9.1.3](#).

Subjects who experience a DLT in Part 1, Cycle 1 must be withdrawn from study treatment and will not be replaced. Subjects enrolled in Part 1 who discontinue from study treatment for reasons other than a DLT prior to completion of the DLT assessment period ([Section 3.2.3](#)) may be replaced. AEs that meet the definition of a DLT that are reported after Cycle 1 will be taken into consideration for dose escalation decisions and to help determine the dose for further investigation in Part 2.

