Subjects who do not experience a DLT in Part 1, Cycle 1 (Dose Escalation) must receive all of their scheduled doses (Days 1, 8, and 15) with completed follow-up data available through 28 days of Cycle 1 to be eligible for DLT assessment. Subjects in Part 1, Cycle 1 who miss a dose for non-AE-related reasons will be replaced.

Both hematologic and non-hematologic DLTs include the following:

- Any AE that prevents the subject from receiving all planned doses during Cycle 1 (Doses may be held up to 7 days for resolution of non-DLT toxicity).
- Any AE that delays the initiation of Cycle 2 by >7 days because the AE has not resolved per criteria required for initiation of a new cycle ([Section 6.1.2](#) and [Section 6.1.4](#)).

Hematologic DLTs include the following:

- Grade 3 or 4 neutropenia (absolute neutrophil count [ANC] <1.0 × 10⁹/L) with a single temperature of >101°F (38.3°C), or microbiologically or radiographically documented infection.
- Grade 4 neutropenia (ANC <0.5 × 10⁹/L) in the absence of fever or infection lasting >7 consecutive days (complete blood count with differential must be measured every 2 to 3 days until recovery of ANC to ≤Grade 2).

- Grade 4 thrombocytopenia (platelet [PLT] count $<25 \times 10^9/L$) lasting >7 days (platelet counts must be measured every 2 to 3 days until recovery to \leq Grade 2 thrombocytopenia).
- Grade 3 or 4 thrombocytopenia (PLT count $<50 \times 10^9/L$) associated with clinically significant bleeding requiring platelet transfusion.

Non-hematologic DLTs include the following:

- Any non-hematologic AE \geq Grade 3, except the following:
 - Nausea, vomiting, diarrhea, electrolyte/metabolic abnormalities, constipation, fever, fatigue, or skin rash that resolves to \leq Grade 2 within 72 hours in the setting of optimal supportive care.
 - Grade 3 elevation in amylase or lipase without clinical or imaging manifestations of acute pancreatitis. In contrast, Grade 4 elevation in amylase or lipase and symptomatic Grade 3 lipase or amylase elevation are considered DLTs.
- Clinical signs and symptoms of acute pancreatitis.

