#### Definition of DLT

A DLT is defined as an AE or abnormal laboratory value that occurs during the first 28 days of treatment and meets the criteria listed below, unless it is assessed to be related to disease, disease progression, intercurrent illness, or concomitant medications.

Toxicities will be assessed by the Investigator using the NCI CTCAE Version 5.0. AEs that are not listed on the NCI CTCAE are to be assessed using the criteria in [Protocol Section 9.1.2](#). The attribution of an AE to KZR-261 is to be assessed by the Investigator using the criteria in [Protocol Section 9.1.3](#).

DLTs will be assessed in Cycle 1. Subjects who experience a DLT after the first, second, or third dose of KZR-261 will be counted as having a DLT but must be withdrawn from the study and will not be replaced. For subjects receiving study drug beyond Cycle 1, any late toxicities that occur after the DLT period (Cycle 1) will be assessed to determine the final MAD/RP2D to be carried forward in the dose expansion phase.

Subjects who do not experience a DLT in Part 1 Cycle 1 (Dose Escalation) must receive all of their scheduled doses (Days 1, 8, and 15) during the DLT assessment period with completed follow-up data available through 28 days of Cycle 1 to be eligible for DLT assessment (ie, DLT-assessable). Subjects in Part 1 Cycle 1 who miss a dose for non-AE-related reasons may be included in the DLT assessment period upon review by the Medical Monitor.

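### The dose-escalation table and the MTD estimator count enrolled or treated subjects, while DLT assessment and the MTD definition count DLT-evaluable subjects; the SAP and protocol also disagree on missed doses

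*Protocol*

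**What the plan says.** **Decision rule.** Protocol 3.2.1 makes Table 1 the basis for dose decisions: "The determination of the dose escalation or dose de-escalation will be based on the algorithm as described in" Table 1. Its columns "represent the number of subjects enrolled at a given dose, and the row represents the number of DLTs at the same dose". The sentence introducing the table uses a different count; it "lists the decisions for up to 12 subjects treated at a given dose". SAP 4.1.1 repeats the enrolled wording. Protocol 10.5.1 and SAP 12 define n_d as subjects treated at dose d.

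**Evaluability.** Under Protocol 3.2.3, a subject without a DLT "must receive all of their scheduled doses (Days 1, 8, and 15) with completed follow-up data available through 28 days of Cycle 1"; otherwise that subject does not qualify for the DLT evaluation. SAP 6.3 has the same rule. Protocol 3.2.4 and SAP 4.1.1 define the MTD as a DLT rate of at most 35% in at least 6-12 DLT-evaluable subjects.

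**Replacement.** Under Protocol 3.2.3, Part 1 subjects who "discontinue from study treatment for reasons other than a DLT prior to completion of the DLT assessment period" may be replaced, and those "who miss a dose for non-AE-related reasons will be replaced". SAP 4.1.1 says instead that subjects "who miss a dose for non-AE-related reasons may be included in the DLT assessment period upon review by the Medical Monitor". SAP 1 says its methods supersede the protocol's; SAP 19 declares no changes.

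**Cohort size.** Protocol 3.2.1 plans "a typical cohort size of 2-4, and 6 to approximately 12 subjects dosed at the putative MTD or MAD".

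**The concern.** The text defining the Table 1 columns and n_d never refers to the evaluable set, and nothing says that a replaced subject leaves the count. SAP 12 mentions the DLT analysis set for summaries and is silent on which set feeds the estimator.

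The i3+3 rule runs on x/n. A non-evaluable subject has, by definition, no DLT. Counting that subject raises n and leaves x alone, so x/n can fall but never rise. Any error is therefore in the less conservative direction.

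Two things are at stake: the escalate, stay or de-escalate decision once a cohort has been topped up, and the MTD, whose identification is a primary endpoint of Part 1. The missed-dose conflict adds a second route. The same subject can be replaced under the protocol and counted under the SAP, which is how the denominator becomes inflated.

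**Working it through.** **1. Which count each section uses**

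| Place | Count |
|---|---|
| Protocol 3.2.1 and SAP 4.1.1, Table 1 columns | enrolled |
| Protocol 3.2.1, sentence introducing Table 1, and the table title | treated |
| Protocol 10.5.1 and SAP 12, n_d | treated |
| Protocol 3.2.3 and SAP 6.3, DLT assessment | evaluable |
| Protocol 3.2.4 and SAP 4.1.1, MTD definition | evaluable |

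| Cycle 1 dose missed for a non-AE reason | Treatment |
|---|---|
| Protocol 3.2.3 | replaced |
| SAP 6.3 and the preceding sentence of SAP 4.1.1 | not DLT-assessable |
| SAP 4.1.1, last sentence on DLTs | may be counted on Medical Monitor review |

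**2. Reproduce Table 1.** Rule from Protocol 10.5.1, with equivalence interval [0.25, 0.35]:

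- x/n below the interval: E. Inside: S.
- Above: S if (x−1)/n is below the interval, otherwise D.
- D becomes DU if Pr(p > 0.30 | x, n) > 0.95.

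The documents give no prior for the DU rule. With an assumed Beta(1,1) prior, all 90 printed cells match. With the Beta(0.005, 0.005) prior of SAP 12, 89 match (5/9 becomes D).

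**3. Count one extra DLT-free subject.** Compare the printed cell at (x, n) with that at (x, n+1) for n = 1 to 11. There are n+1 values of x at each n, so 2 + 3 + … + 12 = 77 comparisons. Ten change, all less cautious; 67 do not.

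| Change | Cells |
|---|---|
| S to E | 1/4→1/5, 2/8→2/9 |
| D to S | 2/4→2/5, 3/8→3/9, 4/11→4/12 |
| DU to D | 2/2→2/3, 3/4→3/5, 4/6→4/7, 5/9→5/10, 6/11→6/12 |

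With up to 4 counted, the only change is 2/2. With two or three extra subjects, changes other than 2/2 again start at 5 counted (for example 1/3 S → 1/5 E).

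**4. Probability of an Escalate reading.** X ~ Bin(n, p), with n evaluable, read at column n and then at column n+1.

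- n = 4: column 4 escalates at X = 0, column 5 at X ≤ 1.
  - p = 0.30: 0.7⁴ = 0.240; adding 4(0.3)(0.7³) = 0.412 gives 0.652.
  - p = 0.40: 0.130 to 0.475.
- n = 8: column 8 escalates at X ≤ 1, column 9 at X ≤ 2.
  - p = 0.30: 0.255 to 0.552.
  - p = 0.40: 0.106 to 0.315.
- n = 1, 2, 3, 5, 6, 7, 9, 10, 11: no change.

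**5. SAP 12 estimator.** p̂ = (x + 0.005)/(n + 0.01), before isotonic regression, against the 0.35 limit, for 6 to 11 evaluable plus one. It crosses the limit at two points only:

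- 3/8: 3.005/8.01 = 0.375; with one more, 3.005/9.01 = 0.334.
- 4/11: 4.005/11.01 = 0.364; with one more, 4.005/12.01 = 0.333.

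On evaluable subjects, 3/8 = 37.5% and 4/11 = 36.4% both fail the MTD definition in SAP 4.1.1. At a true rate of 40%, P(p̂ ≤ 0.35) goes from 0.315 to 0.594 with 8 evaluable and from 0.296 to 0.533 with 11. It does not change at 6, 7, 9 or 10.

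**The case against.** The strongest reply is that the documents, read as a whole, already mean evaluable subjects. Protocol 3.2.3 makes a subject who misses doses ineligible for DLT assessment; Protocol 3.2.1.1 has the SRC review those who completed the DLT period and wait for added subjects to complete it; SAP 6.3 defines an evaluable population. An AE that prevents the planned Cycle 1 doses is itself a DLT, so non-evaluability arises mostly for non-AE reasons. The design only guides decisions, the SRC must agree to every escalation (Protocol 3.5), and its Charter, not available here, may fix the count. The probabilities come from the few affected sizes, and passing 0.35 is not selection as MTD, since isotonic regression and closeness to 0.30 follow. Finally, the supersession clause concerns analysis methods, whereas replacement is trial conduct.

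Much of this stands. An evaluable denominator is clearly intended, most cells do not move, and five of the ten changes remain de-escalations with the level chosen by the SRC. It is also true that SAP 12 does not expressly exclude the evaluable set from the estimator.

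It does not correct the written rule. A subject who misses a dose can still complete 28 days, so the SRC review wording does not enforce the three-dose requirement. Withdrawal, progression and scheduling remain ordinary reasons for non-evaluability. The SRC does not alter the definition of n_d in SAP 12. The missed-dose conflict is explicit whatever one makes of the denominator, and whether a subject is counted is an analysis-set question even if replacement is not.

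**Conclusion.** The concern holds and should be fixed. The stated counting rule is wrong for its purpose, and the two documents give different answers for a subject who misses a dose for a non-AE reason.

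The effect is confined. In typical cohorts of 2-4 no escalate or stay decision changes. It matters when a replacement takes a cohort from 4 to 5, and at the putative MTD or MAD, where the affected sizes of 8 and 11 evaluable fall within the planned range.

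The figures are for one look at one dose, given that one DLT-free non-evaluable subject is counted, before any SRC override. The true DLT rates of 30% and 40% are illustrative: the target and a value above it. The MTD figures stop before isotonic regression. The documents give no rate of non-evaluable subjects, so no unconditional probability can be offered.

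**What to change.** In Protocol 3.2.1, the Table 1 heading, 10.5.1 and 10.5.2, and in SAP 4.1.1 and 12, state: *Table 1 columns, n_d and x_d count only DLT-evaluable subjects (Protocol 3.2.3, SAP 6.3) at their originally assigned dose; replaced non-evaluable subjects are excluded.*

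Change the SAP 4.1.1 sentence on doses missed for non-AE reasons so that such subjects are not evaluable and are replaced, as in Protocol 3.2.3 and SAP 6.3.

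The cost is wording in both documents. In practice a cohort will occasionally wait for a replacement subject before the SRC meets.

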3.2.1.1. Dose Level Escalation for Each Cohort (X+1)

Increments in dose escalation or whether to de-escalate will be based on review of emerging safety data by a SRC composed of study Investigators and Sponsor representatives ([Section 3.5](#)). At a minimum, the SRC will convene upon completion of each successive cohort. The SRC will review safety and available PK data from subjects enrolled to the most recently completed dose cohort who have completed the DLT assessment period. Dose increments for the next cohort will be determined based on the following criteria:

Up to a 100% dose increment may occur if:

- no subject in the most recent cohort required dose reduction for purposes of managing AEs and/or laboratory abnormalities;
- no subject experienced AEs greater than Grade 2 in severity;
- no subject exhibited one or more treatment-emergent serum amylase or lipase $>1.5 \times$ the upper limit of normal (ULN) lasting longer than 72 hours after dosing;

- no subject exhibited fasting blood sugar (FBS) >200 mg/dL on 2 consecutive measures over a 72-hour period after dosing; or
- no subject exhibited FBS >160 mg/dL three or more times over a 72-hour period after dosing.

Up to a 50% dose increment may occur if:

- no subject in the most recent cohort required dose reduction for purposes of managing AEs and/or laboratory abnormalities;
- there is resolution of any \geq Grade 3 AE to Grade 1 or baseline in ≤ 10 days

Up to a 33% dose increment may occur if:

- no subject in the most recent cohort required dose reduction for purposes of managing AEs and/or laboratory abnormalities;
- there is no resolution of any \geq Grade 3 AE to Grade 1 or baseline within 10 days.

AEs for dose increment decisions must be treatment-emergent and considered at least possibly related to KZR-261.

Lower dose increases (ie, 25% increase or $1.25 \times$ *current dose*) may be considered based on the frequency and severity of AEs not described above that are at least possibly related to KZR-261.

If a DLT necessitates enrollment of additional subjects into a cohort, all safety data for that cohort will be reviewed after the additional subjects have completed the DLT assessment period. Based on evaluation of the data, the SRC and/or Sponsor may decide to enroll subjects at a KZR-261 dose level that is intermediate between the previous and the next higher planned dose.

If a slot within the current dose escalation cohort is not available, additional subjects may be treated at a lower dose level deemed by the SRC to be safe and adequately tolerated. Subjects with malignant melanoma, malignant mesothelioma, mCRPC, or mCRC are preferred but not required for backfilling.

The SRC can recommend enrollment of additional subjects at the putative MTD or MAD dose level to further assess safety at this dose.

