3.5. Safety Review Committee (Parts 1, 2A, and 2B)

The SRC will consist of the Medical Monitor (or designate), other Kezar representative(s), and participating Investigators. All Investigators who enroll subjects in the cohort under review will be consulted prior to the SRC meeting if they are unable to attend the scheduled meeting.

During Part 1, the committee will review safety data from the current cohort and previous cohorts before deciding on escalation to the next dose level. Dose escalation may occur only after the SRC has agreed ([Section 3.2.1.1](#)).

The totality of safety data from Part 1 will be reviewed prior to a declaration of the MTD/MAD. Available PK data may also be reviewed.

During Parts 2A and 2B, the SRC will periodically monitor safety data through the end of the study.

In Part 2, the study will be halted if there is one Grade 5 or two Grade 4 AEs in different subjects that are considered at least possibly related to KZR-261. Exceptions to the halting criteria include asymptomatic Grade 4 laboratory abnormalities (eg, neutropenia) that resolve either with or without routine supportive care measures and without sequelae. If this scenario occurs, a formal safety analysis will be conducted, and the findings will be submitted to the IND for the FDA to review prior to enrolling additional subjects.

A separate SRC Charter will describe the responsibilities of this committee for both dose escalation and dose expansion/dose optimization.

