6.1.4.2. Dose Modifications for Toxicity

Outside the DLT assessment period, dose modifications are to be discussed with the Medical Monitor prior to implementation to determine whether a dose modification is recommended. If KZR-261 is withheld for any toxicity within a treatment cycle, KZR-261 may be resumed **within that cycle** pending fulfillment of the criteria in [Section 6.1.2](#) to Grade 1 or baseline, platelet counts to Grade 2 without clinical bleeding, or absolute neutrophil counts to Grade 2 prior to the next scheduled treatment.

[Table 2](#) through [Table 7](#) summarize guidelines for KZR-261 treatment modifications for various potential toxicities encountered. The dose modifications detailed in these tables are based on toxicities encountered within a cycle to determine the most appropriate dose for initiation of a

subsequent treatment cycle (assuming that all the retreatment criteria for a new cycle as summarized in [Section 6.1.3](#) are met). Any dose reductions should be discussed with the Medical Monitor and documented in the source file and the eCRF.

Table 2: Dose Modifications for Isolated Transaminase Elevations

NCI-CTC AE Grade	Dose Adjustment
First episode of \geq Grade 3 ($>5\times$ baseline). Check transaminases at least twice per week until peak levels are reached, and then no less than weekly.	Withhold dose Resume dosing when elevations resolve to \leq Grade 2 and: 
• Reduce KZR-261 dose by one level if within a cycle• Subsequent cycles will begin at the reduced dose level
Second episode of \geq Grade 3 ($>5\times$ baseline). Check transaminases at least twice per week until peak levels are reached, and then no less than weekly.	Withhold dose Resume dosing at the subject's baseline grade and: 
• Reduce KZR-261 dose by one more level if within a cycle• Subsequent cycles will begin at the reduced dose level
Third episode of \geq Grade 3 ($>5\times$ baseline). Check transaminases at least twice per week until peak levels are reached, and then no less than weekly.	Discontinue KZR-261. Subject is not eligible to resume treatment.

Abbreviations: NCI CTCAE=Common Terminology Criteria for Adverse Events

Toxicity grades are per CTCAE v5.

Table 3: Dose Modifications for Thrombocytopenia

NCI CTCAE Grade	Dose Adjustment
Grade 3 thrombocytopenia with resolution to \leq Grade 2 within 1 week	No dose adjustment for subsequent cycles

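### Protocol 3.2.1.1 joins the five conditions for a 100% dose increment with 'or', so as written the 50% and 33% caps never bind

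*Protocol*

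**What the plan says.** Protocol 3.2.1.1 bases the size of the next dose step on three tiers. Only treatment-emergent AEs at least possibly related to KZR-261 count.

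- **Up to 100%.** Five conditions, here labelled A to E:
  - A: "no subject in the most recent cohort required dose reduction for purposes of managing AEs and/or laboratory abnormalities"
  - B: no AE above Grade 2
  - C: no amylase or lipase above 1.5 × ULN for longer than 72 hours
  - D: no fasting blood sugar (FBS) above 200 mg/dL "on 2 consecutive measures over a 72-hour period after dosing; or"
  - E: no FBS above 160 mg/dL three or more times in 72 hours
- **Up to 50%.** Condition A again, plus resolution of any Grade 3 or higher AE to Grade 1 or baseline in at most 10 days.
- **Up to 33%.** Condition A again, plus no resolution of any "Grade 3 AE to Grade 1 or baseline within 10 days".

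The section does not say that all five conditions are needed for 100%, or which tier governs when a cohort meets more than one. The SAP does not restate the criteria. SAP Table 2 lists dose levels and percent increases only.

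Other provisions constrain escalation. Protocol 3.2.1 says of Table 1: "The determination of the dose escalation or dose de-escalation will be based on the algorithm as described in" that table. Protocol 3.5 adds: "Dose escalation may occur only after the SRC has agreed".

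**The concern.** A list of separate conditions ending in *or* ordinarily means that any one is enough. The protocol follows that usage elsewhere. The Part 1 stopping conditions in Protocol 10.1.1 are introduced as one of three and also carry *or* before the last item. Where every element is needed, as in the Hy's law criterion in Protocol 3.2.3, the text says so and uses a capitalised AND.

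On that reading the tiers lose their function. Condition A belongs to all three, so meeting a lower tier already satisfies one of the five conditions for 100%. A cohort with a slow-resolving related Grade 3 AE would have the same ceiling as a cohort with no findings. These criteria are meant to hold back the step size in a first-in-human study, and the pancreatic and glucose items track toxicities seen in monkeys (Protocol 1.2.3.1).

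**Working it through.** **1. The plan's own figures.** The SAP Table 2 doses are 1.8, 3.6, 7.2, 12, 18, 27, 40, 60 and 80 mg/m². With increase = 100 × (dose / previous dose − 1), the steps are 100.0, 100.0, 66.7, 50.0, 50.0, 48.1, 50.0 and 33.3%. The table states 100, 100, 67, 50, 50, 50, 50 and 33%. All agree within 2 points.

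**2. The logic.** Let A to E be true when the condition is met. Related Grade 3 or higher AEs have three states: none, all resolved within 10 days, or not. B is true only for none.

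- Literal 100% tier: A or B or C or D or E.
- 50% tier: A, and none or all resolved.
- 33% tier: A, and not resolved.

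Both lower tiers require A, and A alone opens the literal 100% tier, so neither lower cap can bind.

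**3. Enumeration.** There are 2 (A) × 3 (AE state) × 2 × 2 × 2 (C, D, E) = 48 states. In 24 of them a lower tier is met.

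| Reading of the 100% list | States with 100% open | Lower cap binds, of 24 |
|---|---|---|
| Any one condition (literal) | 46 | 0 |
| All five | 1 | 23 |
| A, B and C, with either D or E | 3 | 21 |

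These counts show the logic and are not probabilities.

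**4. Where a dose reduction was required.** Reductions are barred in Cycle 1 of Part 1 (Protocol 6.1.4), so on Cycle 1 data A is nearly always met. Protocol 6.1.4.2, however, uses "toxicities encountered within a cycle to determine the most appropriate dose for initiation of a" subsequent cycle, so a Cycle 1 toxicity can lead to a reduction at the start of Cycle 2. A then fails and both lower tiers close. The literal 100% tier stays open if any of B to E holds. It closes only when B, C, D and E all fail too, which is 2 of the 48 states.

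**5. A case that can reach escalation.** Take related Grade 3 fatigue after the Day 15 dose. Protocol 3.2.3 exempts from the DLT definition certain events, including "constipation, fever, fatigue, or skin rash that resolves to" Grade 2 or lower within 72 hours with optimal supportive care. If the fatigue reaches Grade 2 in that time but needs more than 10 days to reach Grade 1, it is not a DLT on that criterion and fails the 10-day test. Table 7 allows treatment to resume at the same dose, so a reduction need not be required. If Table 1 says escalate, the ceilings from 7.2 mg/m² are:

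- Intended, 33%: 7.2 × 1.33 = 9.6 mg/m²
- Literal, 100%: 7.2 × 2 = 14.4 mg/m²
- Listed next dose in SAP Table 2: 12.0 mg/m²

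The listed dose exceeds the intended ceiling (12.0 / 9.6 = 1.25) but lies within the literal one.

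**The case against.** The best defence is that nobody would apply the rule this way. Three descending tiers of no-subject conditions make sense only if the conditions are cumulative. The 50% and 33% lists carry no connective, and they are read here as joint. That is fair on intent. It does little for the text: a lower cap can bind only where the 100% tier is closed, which is 2 of 48 states however the lower lists are joined.

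A second defence is that *or* links only the two glucose items. The lower caps then bind again, but a cohort with two consecutive FBS values above 200 mg/dL would still pass if it had no third value above 160. That cannot be intended either.

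Third, the controls are real. The tiers say what may be done, up to a limit. Table 1 must permit escalation and the SRC must agree. Smaller steps are available, and the SAP ladder tapers to 50% or less from 12.0 mg/m² upward. The SRC Charter is not among the documents and may be clearer. All of this lowers exposure, but none of it corrects the criteria that the SRC is told to use.

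Four stronger inferences are tempting and do not hold:

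- *The pancreatic and glucose thresholds limit nothing.* They do not restrict the increment when no reduction was required. When a reduction was required and a related Grade 3 or higher AE occurred, they alone decide whether the literal 100% tier is open.
- *Most of the dose ladder is affected.* Comparing listed steps with 50% or 33% caps describes the planned ladder. The result would be the same if the word were *and*.
- *Repeated FBS values above 160 mg/dL would routinely expose the error.* Scheduled fasting chemistry after the first Cycle 1 dose falls on Days 8, 15, 22 and 28 (Appendix A). Three values within 72 hours of a dose would need unscheduled tests.
- *Cohorts were, or were meant to be, doubled on one condition.* Nothing in the documents shows this.

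**Conclusion.** The concern holds as a drafting error in an operative safety rule. As written, the 50% and 33% caps bind for no cohort. For cohorts with no required dose reduction, the AE-grade, amylase/lipase and glucose conditions do not restrict the increment. After a required reduction the lower tiers close, while the literal 100% tier can stay open on any other condition.

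In the worked case the literal ceiling is 14.4 mg/m² against an intended 9.6 mg/m², a ratio of 1.5. This rests on the ordinary meaning of a list ending in *or*, and on reading the two lower lists as joint conditions. The fatigue case is narrow, and the documents give no rate for such cohorts, so no frequency is claimed. The correction is worth making because the rule gives the wrong ceiling if followed as written and nothing in the protocol or SAP overrides it.

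**What to change.** In Protocol 3.2.1.1:

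1. Reword the lead-in so that an increment of up to 100% is allowed only if all of the following are met, and change *or* to *and*.
2. State that the most restrictive applicable tier governs. A cohort with no required dose reduction that fails any other 100% condition is capped at 50%. The cap is 33% if any related Grade 3 or higher AE did not resolve to Grade 1 or baseline within 10 days.
3. Add no new allowance for escalating after a required dose reduction. On the intended reading all three tiers are closed in that case. The existing flexibility does not clearly cover it: the 25% step is for AEs not otherwise described, and the option of a "dose level that is intermediate between the previous and the next higher planned dose" sits in a paragraph about enlarging a cohort after a DLT.

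The cost is a short wording amendment with the usual IRB approval. Sample size, visits and data collection do not change.
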